## 6.0 Dose Modification for Adverse Events

### 6.1 Anticipated Toxicities

#### 6.1.1 Ibrutinib

Per the package insert (January 2019) the expected toxicities for ibrutinib are as follows:

System Organ Class	Adverse Reactions
Gastrointestinal disorders	
Very common	Nausea, diarrhea, vomiting, constipation, abdominal pain, stomatitis, dyspepsia
Frequency not known	Gastrointestinal esophageal reflux disease
Infections and infestations	
Very common	Infection a , upper respiratory tract infection, sinusitis, pneumonia, urinary tract infection, skin infection
Frequency not known	Hepatitis B reactivation
Blood and lymphatic system disorders	
Very common	Neutropenia, thrombocytopenia
Common	anemia
Cardiac disorders	
Very Common	Ventricular tachyarrhythmias a
Common	Atrial fibrillation
Immune system disorders	
Frequency not known	Anaphylactic reaction, angioedema, urticaria
Metabolism and nutrition disorders	
Common	Decreased appetite, dehydration, hypoalbuminemia, hypokalemia, hyperuricemia
Frequency not known	Tumor lysis syndrome
Nervous system disorders	
Very common	Dizziness, headache
Frequency not known	Peripheral neuropathy
Respiratory, thoracic and mediastinal disorders	
Very common	Cough, dyspnea, epistaxis, oropharyngeal pain
Frequency not known	Interstitial lung disease a
Hepatobiliary disorders	
Frequency not known	Acute hepatic failure, hepatic cirrhosis
Eye disorders	

System Organ Class	Adverse Reactions
Very common	Blurred vision
Skin and subcutaneous tissue disorders	
Very common	Rash a , pruritus, bruising, petechiae
Frequency not known	Stevens-Johnson syndrome, panniculitis, onychoclasia
Musculoskeletal and connective tissue disorders	
Very common	Musculoskeletal pain a , myalgia, muscle spasms
Neoplasms, benign malignant and unspecified	
Very common	Secondary malignancy
General disorders and administration site conditions	
Very common	Fatigue, pyrexia, peripheral edema, asthenia, chills
Vascular disorders	
Very common	Hypertension, hemorrhage a
Investigations	
Very common	Weight decreased

a Represents pooling of preferred terms

Very common ( $\geq 1/10$ ); Common ( $\geq 1/100$  to  $< 1/10$ ); Uncommon ( $\geq 1/1,000$  to  $< 1/100$ ); Rare ( $\geq 1/10,000$  to  $< 1/1,000$ ); Very rare ( $< 1/10,000$ ); not known (cannot be estimated from the available data).

Refer also to [Section 2.4.2](#).

#### 6.1.2 Brentuximab Vedotin

Per the IB (version 16, October 2018) the expected toxicities for brentuximab vedotin are as follows:

System Organ Class	Adverse Reactions
Infections and infestations	
Very common	Infection a , upper respiratory tract infection
Common	Herpes zoster, pneumonia, herpes simplex, oral candidiasis
Uncommon	Pneumocystis jiroveci pneumonia, staphylococcal bacteremia, cytomegalovirus infection or reactivation, sepsis/septic shock
Frequency not known	Progressive multifocal leukoencephalopathy
Blood and lymphatic system disorders	
Very common	Neutropenia
Common	Anemia, thrombocytopenia
Uncommon	Febrile neutropenia
Immune system disorders	
Uncommon	Anaphylactic reaction
Metabolism and nutrition disorders	
Common	Hyperglycemia
Uncommon	Tumor lysis syndrome
Nervous system disorders	
Very common	Peripheral sensory neuropathy, peripheral motor neuropathy

System Organ Class	Adverse Reactions
Common	Dizziness
Uncommon	Demyelinating polyneuropathy
Respiratory, thoracic and mediastinal disorders	
Very common	Cough, dyspnea
Gastro-intestinal disorders	
Very common	Nausea, diarrhea, vomiting, constipation, abdominal pain
Uncommon	Pancreatitis acute
Hepatobiliary disorders	
Common	Alanine aminotransferase/aspartate aminotransferase increased
Skin and subcutaneous tissue disorders	
Very common	Rash a , pruritus
Common	Alopecia
Uncommon	Stevens-Johnson syndrome/toxic epidermal necrolysis
Musculoskeletal and connective tissue disorders	
Very common	Arthralgia, myalgia
Common	Back pain
General disorders and administration site conditions	
Very common	Fatigue, pyrexia, infusion-related reactions a
Common	Chills
Investigations	
Very common	Weight decreased

a Represents pooling of preferred terms

Very common ( $\geq 1/10$ ); Common ( $\geq 1/100$  to  $< 1/10$ ); Uncommon ( $\geq 1/1,000$  to  $< 1/100$ ); Rare ( $\geq 1/10,000$  to  $< 1/1,000$ ); Very rare ( $< 1/10,000$ ); not known (cannot be estimated from the available data).

## 6.2 Dose Modifications

Given that brentuximab vedotin has demonstrated activity in this disease setting, ibrutinib should be preferentially dose reduced in the event of toxicity. The only exception is in the event of peripheral motor or sensory neuropathy, in that case, brentuximab vedotin dose will be reduced 1st given its direct correlation to brentuximab vedotin.

### Ibrutinib (supplied by Pharmacyclics):

#### Interrupt or discontinue therapy

- Interrupt therapy for any non-hematological toxicity  $\geq$ Grade 3, neutropenia with infection or fever  $\geq$ Grade 3, or Grade 4 hematological toxicities
- Reinitiate ibrutinib at the starting dose (indicated specific) once toxicities have resolved to Grade 1 or baseline (recovery)
- If the toxicity reoccurs, reduce dose by 1 capsule (140 mg/day)
- A second reduction of dose by 140 mg may be considered as needed
- Discontinue if these toxicities persist or recur following 2 dose reductions

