#### **5.1.5 Dose and Administration**

In the lead in phase, an initial dose of ibrutinib 420 mg is given orally once daily. Once that is proven to be safe, we will give 560 mg of ibrutinib orally daily. In the phase II portion, Ibrutinib 560 mg (4 x 140-

mg capsules) is administered orally once daily. The capsules are to be taken around the same time each day with 8 ounces (approximately 240 mL) of water. The capsules should be swallowed intact, and subjects should not attempt to open capsules or dissolve them in water. The use of strong CYP3A inhibitors/inducers, and grapefruit and Seville oranges should be avoided for the duration of the study (See [Appendix 1](#)).

If a dose is not taken at the scheduled time, it can be taken as soon as possible on the same day with a return to the normal schedule the following day. The subject should not take extra capsules to make up the missed dose. A subject diary will be used to aid with as well as document study drug administration compliance. At any given visit, enough ibrutinib capsules to carry the subject to the next visit should be dispensed. Unused ibrutinib capsules dispensed during previous visits must be returned, and drug accountability records should be updated. Returned capsules must not be redispensed to anyone. Subjects should return all empty bottles to the site. Empty bottles should be destroyed at the site or returned to the Sponsor after the site monitor has completed a review of drug accountability.

The first dose will be delivered in the clinic on Day 1, after which subsequent dosing is typically on an outpatient basis. Ibrutinib will be dispensed to subjects in bottles at each visit.

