**Other non-hematological toxicities:** For Grade 1 or 2, continue at same dose. For Grade 3, withhold dose until toxicity is  $\leq$  Grade 1 or has returned to baseline, then resume treatment at the same dose level. For Grade 4, withhold until toxicity  $\leq$  Grade 1 or has returned to baseline, then resume treatment at same dose level but reduce ibrutinib dose from 560 mg to 420 mg. For second occurrence of Grade 3, withhold dose until toxicity  $\leq$  Grade 1 or has returned to baseline, then resume BV at same dose level, but reduce ibrutinib from 560 mg to 420 mg. For second occurrence of Grade 4, withhold until toxicity  $<$  Grade 1 or has returned to baseline, then resume BV at same dose level but reduce ibrutinib from 420 mg to 280 mg. For third occurrence of Grade 3, withhold dose until toxicity  $<$  Grade 1 or has returned to baseline, then resume BV at same dose level but reduce ibrutinib from 420 mg to 280 mg. For third occurrence of grade 4 toxicity, discontinue ibrutinib. In patients with recurrent grade 3 and 4 non hematological toxicities despite dose reduction specified for ibrutinib, then reduce treatment of BV to 1.2 mg/kg. If patient was already at 1.2 mg/kg of BV, then discontinue treatment of BV and ibrutinib.

The start of the next cycle may be delayed for up to 3 weeks if additional time is required for the patient to recover from study treatment-associated toxicity experienced during the current cycle. Delays of greater than 3 weeks are prohibited without approval of the PI.

Doses reduced for drug-related toxicity should generally not be re-escalated. However, intra-patient re-escalation to the previous dose level may be permitted at the discretion of the PI.

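### After a first Grade 4 non-hematologic toxicity other than neuropathy, Section 6.2 restarts a 560 mg patient on ibrutinib at both 560 mg and 420 mg, and does not say which rule governs

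*Combined protocol and SAP*

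**What the plan says.** Section 5.1.5 sets the dose: "In the phase II portion, Ibrutinib 560 mg" once daily, as four 140 mg capsules. Dose level 1 in the lead-in is 420 mg. Under Section 5.1.7, 420 mg would also be the phase II dose if 560 mg is not tolerated.

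Section 6.2 then adjusts ibrutinib in two places.

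- **Ibrutinib heading, Interrupt or discontinue therapy.** The drug is interrupted for any non-hematologic toxicity of Grade 3 or higher, among other triggers. After recovery the instruction is "Reinitiate ibrutinib at the starting dose (indicated specific) once toxicities have resolved to Grade 1 or baseline (recovery". A reduction comes only on recurrence: "If the toxicity reoccurs, reduce dose by 1 capsule (140 mg/day". After that, "A second reduction of dose by 140 mg may be considered as needed".
- **Brentuximab vedotin (BV) heading, Other non-hematological toxicities.** For Grade 4, treatment is held until Grade 1 or lower or baseline, "then resume treatment at same dose level but reduce ibrutinib dose from 560 mg to 420 mg". A separate sentence takes ibrutinib from 420 to 280 mg at the second Grade 4 event. At the third: "For third occurrence of grade 4 toxicity, discontinue ibrutinib". For a second Grade 3 event the text is "then resume BV at same dose level, but reduce ibrutinib from 560 mg to 420 mg".

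Section 6.2 opens with a general principle, "ibrutinib should be preferentially dose reduced in the event of toxicity". Motor or sensory neuropathy is the exception, where BV is reduced first. Peripheral neuropathy has its own paragraph.

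**The concern.** Both places direct the same drug, for the same patient, after the same event, and they give different doses. The category affected is the most severe non-fatal one. This is a multi-center trial, so two sites could each follow a written rule and restart patients at different ibrutinib doses after a life-threatening toxicity. A monitor could not say which site had deviated.

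The layout adds to the risk. The stricter rule for ibrutinib sits under the BV heading, so a site looking up the ibrutinib dose would naturally read the ibrutinib bullets and stop there. What is at stake is dosing safety and consistency across sites.

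**Working it through.** No sample-size or power figure bears on this, so the check applies each rule step by step, using 140 mg per capsule.

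**Do both rules cover the event?** The ibrutinib bullets apply to any non-hematologic toxicity of Grade 3 or higher, which includes Grade 4. The other paragraph names Grade 4. Its separate sentence for a second Grade 4 event shows that the 420 mg step belongs to the first. Peripheral neuropathy falls outside that paragraph and is excluded here.

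**Patient assigned 560 mg**

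| Event | Ibrutinib bullets | Toxicity paragraphs in the BV block | Compatible? |
|---|---|---|---|
| First Grade 4 other non-hematologic | 560 mg | 420 mg | No: 560 − 420 = 140 mg/day; 140/560 = 25% |
| Same toxicity again at Grade 4 | 560 − 140 = 420 mg | 280 mg | No: 420 − 280 = 140 mg/day |
| Third Grade 4 | second 140 mg reduction optional | stop | Not counted as a conflict |
| Grade 3 other non-hematologic, events 1/2/3 | 560/420/280 mg (last optional) | 560/420/280 mg | Yes |
| Grade 4 anemia or thrombocytopenia, events 1/2/3 | 560/420/280 mg (last optional) | 560/420/280 mg | Yes |

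The second row assumes that one toxicity recurs. The bullets act on recurrence of the toxicity, whereas the other paragraph counts Grade 4 occurrences. The last two rows show that the rules agree elsewhere, so the conflict is specific to Grade 4 non-hematologic toxicity.

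**Does any text set precedence?** The opening of Section 6.2 ranks ibrutinib against BV for reduction. It does not rank the two ibrutinib schedules against each other. The paragraph on giving the two drugs together deals with timing. The closing lines of Section 6.2 deal with cycle delay and re-escalation. None of these settles the question.

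**Patient assigned 420 mg (minor)**

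- At a second Grade 3 other non-hematologic event, or a second Grade 4 anemia or thrombocytopenia, the bullets give 420 − 140 = 280 mg. The toxicity paragraphs describe a step from 560 to 420 mg, which does not fit this patient.
- At a first Grade 4 other non-hematologic event the bullets give 420 mg. The toxicity paragraph ends at 420 mg but again describes a step from 560 mg.
- Two 140 mg reductions would take the patient to 420 − 280 = 140 mg. The absolute steps go no lower than 280 mg.

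Under the 3+3 rules, planned exposure at 420 mg is 3 to 6 lead-in patients, and more only if 560 mg is not tolerated.

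**The case against.** The strongest answer is that Section 6.2, read as a whole, already points to 420 mg. It opens by preferring ibrutinib reduction. The Grade 4 text is specific to grade and occurrence, while the starting-dose bullet is generic. This stands as evidence of intent, but it is an inference and not a written rule. The position of the Grade 4 text under the BV heading works against it.

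Safeguards also reduce the harm:

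- Both rules hold ibrutinib until Grade 1 or baseline.
- A life-threatening event is a serious adverse event (Section 13.1.2), reported within 24 hours during treatment (Section 13.3.2.1). Reports from sites outside the coordinating center are forwarded immediately to the study PI (Section 13.3.3.1).
- Section 6.2 lets the PI permit re-escalation, so 560 mg after a Grade 4 event is not ruled out.

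These points stand and limit the severity. They do not remove the contradiction, and a Grade 4 laboratory value that is not a serious event could escape that reporting route.

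A reader might infer more than the documents support:

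- **That the rules also clash at the third Grade 4 event.** The second reduction in the ibrutinib bullets is optional, so stopping need not breach them.
- **That patients on 420 mg are denied a reduction.** A step from 560 mg is simply inapplicable to them, and the bullets' relative 140 mg step can fill the gap.
- **That the problem will arise often.** The documents give no Grade 4 non-hematologic rate for the combination, so no frequency can be used to argue severity.

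**Conclusion.** The contradiction is real and narrow. For a patient on 560 mg with a first Grade 4 non-hematologic toxicity other than peripheral neuropathy, one rule restarts ibrutinib at 560 mg and the other at 420 mg. That is a difference of 140 mg/day, or 25%. It remains one capsule at the next step if the same toxicity recurs at Grade 4. The conclusion takes the starting dose to be the dose assigned in the protocol. The bullet's parenthetical qualifier is unclear, but Section 5.1.5 leaves no other candidate in phase II.

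The evident intent is 420 mg and the harm is bounded. It is still worth correcting, because two safety instructions contradict each other and the correction costs little. A reader might infer that the efficacy design is compromised. It is not: the stage sizes, response cut-offs and error rates of the Simon design do not depend on which restart dose applies. The mismatch for patients assigned 420 mg is a minor drafting point.

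**What to change.** 1. In the ibrutinib bullets of Section 6.2, limit restarting at the starting dose to first events other than Grade 4 non-hematologic toxicity.
2. State that for Grade 4 non-hematologic toxicities other than peripheral neuropathy the schedule under Other non-hematological toxicities governs: 560 to 420 mg at the first event, 420 to 280 mg at the second, discontinue at the third. The clinical team should confirm that this is the intent.
3. State that neuropathy stays under the exception at the start of Section 6.2 and its own paragraph. Without this, the new sentence would conflict with the rule that reduces BV first.
4. For patients assigned 420 mg, add that the relative 140 mg step applies at a second Grade 3 non-hematologic event or a second Grade 4 anemia or thrombocytopenia. The clinical team should set their step at a first Grade 4 non-hematologic event and their lowest allowed dose (140 or 280 mg).

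The cost is a text amendment to Section 6.2 with the usual IRB and Pharmacyclics review, plus the clinical decisions in items 2 and 4. It needs no extra patients, visits or procedures, and no change to the statistical design.

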#### Hepatic impairment

- Mild (Child Pugh class A): 140 mg PO qDay
- Moderate-to-severe (Child Pugh Classes B and C): Avoid use

**Brentuximab vedotin and Ibrutinib:**

If either agent were held for toxicities, the next cycle of treatment will be delayed until toxicities become acceptable for both drugs before treatment continues. Both drugs will be given at the start of each cycle. For example, if brentuximab vedotin was dose delayed for peripheral neuropathy for 4 weeks, Ibrutinib dosing will stop after 3 weeks and held. Ibrutinib will be given again when it is deemed acceptable to start brentuximab vedotin. If Ibrutinib was held for thrombocytopenia at D15 and can be resumed at D18, brentuximab vedotin can be given at the original scheduled infusion day. However, if ibrutinib was held at D15 and cannot resume for 2 weeks later, then brentuximab vedotin will only be given at the same time Ibrutinib is restarted.

**Brentuximab vedotin (commercial supply):**

**Peripheral Neuropathy:** Peripheral neuropathy should be managed using a combination of dose delay and reduction to 1.2 mg/kg. For new or worsening Grade 2 or 3 neuropathy, dosing should be held until neuropathy improves to Grade 1 or baseline and then restarted at 1.2 mg/kg. For Grade 4 peripheral neuropathy, BV should be discontinued.

**Neutropenia:** Neutropenia should be managed by dose delays and reductions. For grade 1 or 2, continue at same dose. The dose of BV should be held for Grade 3 or 4 neutropenia until resolution to baseline or Grade 2 or lower. Growth factor support should be considered for subsequent cycles in patients who experience Grade 3 or 4 neutropenia. In patients with recurrent Grade 4 neutropenia despite the use of growth factors, and despite dose reduction specified for ibrutinib, discontinuation or dose reduction of BV to 1.2 mg/kg may be considered.

**Anemia and thrombocytopenia:** For Grade 1 or 2, continue at same dose. For Grade 3 and 4, withhold dose until toxicity is  $\leq$  Grade 2 or has returned to baseline, then resume treatment at the same dose level. For second occurrence of Grade 4, withhold until toxicity  $\leq$  Grade 1 or has returned to baseline, then resume treatment at 1.8 mg/kg but reduce ibrutinib dose from 560 mg to 420 mg. For third occurrence, withhold until toxicity  $\leq$  grade 1 or has returned to baseline, then resume BV at 1.8 mg/kg but reduce ibrutinib dose from 420 mg to 280 mg. In patients with recurrent grade 4 anemia and thrombocytopenia despite dose reduction specified for ibrutinib, then resume treatment of BV at 1.2 mg/kg. If patient was already at 1.2 mg/kg of BV, then discontinue treatment of BV and ibrutinib.

**Other non-hematological toxicities:** For Grade 1 or 2, continue at same dose. For Grade 3, withhold dose until toxicity is  $\leq$  Grade 1 or has returned to baseline, then resume treatment at the same dose level. For Grade 4, withhold until toxicity  $\leq$  Grade 1 or has returned to baseline, then resume treatment at same dose level but reduce ibrutinib dose from 560 mg to 420 mg. For second occurrence of Grade 3, withhold dose until toxicity  $\leq$  Grade 1 or has returned to baseline, then resume BV at same dose level, but reduce ibrutinib from 560 mg to 420 mg. For second occurrence of Grade 4, withhold until toxicity  $<$  Grade 1 or has returned to baseline, then resume BV at same dose level but reduce ibrutinib from 420 mg to 280 mg. For third occurrence of Grade 3, withhold dose until toxicity  $<$  Grade 1 or has returned to baseline, then resume BV at same dose level but reduce ibrutinib from 420 mg to 280 mg. For third occurrence of grade 4 toxicity, discontinue ibrutinib. In patients with recurrent grade 3 and 4 non hematological toxicities despite dose reduction specified for ibrutinib, then reduce treatment of BV to 1.2 mg/kg. If patient was already at 1.2 mg/kg of BV, then discontinue treatment of BV and ibrutinib.

The start of the next cycle may be delayed for up to 3 weeks if additional time is required for the patient to recover from study treatment-associated toxicity experienced during the current cycle. Delays of greater than 3 weeks are prohibited without approval of the PI.

Doses reduced for drug-related toxicity should generally not be re-escalated. However, intra-patient re-escalation to the previous dose level may be permitted at the discretion of the PI.

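### Two steps of the anemia/thrombocytopenia rule restart brentuximab vedotin at a fixed 1.8 mg/kg, which conflicts with the default against re-escalation for a patient already reduced to 1.2 mg/kg

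*Combined protocol and SAP*

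**What the plan says.** Section 6.2 opens by making ibrutinib the drug to reduce first for toxicity. Neuropathy is the one exception, and there BV is cut first. When Grade 2 or 3 neuropathy appears or worsens, the rule for BV reads: "dosing should be held until neuropathy improves to Grade 1 or baseline and then restarted at 1.2 mg/kg".

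The anemia/thrombocytopenia rule has four restart steps for Grade 3 or 4 events:

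- First event: "then resume treatment at the same dose level. For second occurrence of Grade 4" (the quote runs on into the opening of the next step).
- Second Grade 4 event: "then resume treatment at 1.8 mg/kg but reduce ibrutinib dose from 560 mg to 420 mg".
- Third occurrence: "then resume BV at 1.8 mg/kg but reduce ibrutinib dose from 420 mg to 280 mg".
- Recurrent Grade 4 despite the ibrutinib reductions: "then resume treatment of BV at 1.2 mg/kg. If patient was already at 1.2 mg/kg of BV", both drugs are stopped.

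The rule for other non-hematological toxicities uses different wording at the matching points: "then resume BV at same dose level, but reduce ibrutinib from 560 mg to 420 mg", and later "then resume BV at same dose level but reduce ibrutinib from 420 mg to 280 mg".

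Near its end, Section 6.2 states a general default: "Doses reduced for drug-related toxicity should generally not be re-escalated". The next sentence lets the PI permit a return to the previous dose level.

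**The concern.** The two middle steps of the anemia/thrombocytopenia rule name a BV dose in mg/kg instead of referring to the patient's current dose. For a patient at 1.8 mg/kg the two forms mean the same thing. For a patient already at 1.2 mg/kg they do not, because the step as written raises BV in someone who has just had a severe cytopenia and had earlier been reduced for a different toxicity. The steps do not mention PI approval and are not limited to patients still at full dose.

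Section 2.4.1 describes BV neuropathy as following a cumulative pattern and as generally managed by delay and reduction to 1.2 mg/kg. An unintended return to 1.8 mg/kg would undo that management. The Synopsis lists four sites, and they could treat the same patient differently.

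**Working it through.** No planned figure has to be reproduced. The check compares the restart instructions, tests whether the conflict can arise, and sizes it.

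**1. Restart steps in Section 6.2 that state a BV dose and do not reduce BV**

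| Rule | Step | BV restart dose | Ibrutinib |
|---|---|---|---|
| Anemia/thrombocytopenia | First Grade 3 or 4 | same level | unchanged |
| Anemia/thrombocytopenia | Second Grade 4 | **1.8 mg/kg** | 560 to 420 mg |
| Anemia/thrombocytopenia | Third occurrence | **1.8 mg/kg** | 420 to 280 mg |
| Other non-hematological | First Grade 3 | same level | unchanged |
| Other non-hematological | First Grade 4 | same level | 560 to 420 mg |
| Other non-hematological | Second Grade 3 | same level | 560 to 420 mg |
| Other non-hematological | Second Grade 4 | same level | 420 to 280 mg |
| Other non-hematological | Third Grade 3 | same level | 420 to 280 mg |

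Same level: 1 + 5 = 6 of 8. Fixed 1.8 mg/kg: 2 + 0 = 2 of 8.

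The comparison holds only for these eight steps. The neuropathy rule and the final anemia/thrombocytopenia step restart BV at 1.2 mg/kg by design, and the neutropenia rule names no BV dose for its ordinary restart.

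**2. Can a patient at 1.2 mg/kg reach a fixed-dose step?**

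- *Neuropathy.* BV is cut first, so the patient can be at BV 1.2 mg/kg with ibrutinib still at 560 mg. At a second Grade 4 cytopenia the ibrutinib part of the step (560 to 420 mg) applies as written. Only the BV figure does not fit.
- *Neutropenia and other non-hematological toxicity.* Both rules reach 1.2 mg/kg only after ibrutinib has been reduced, so these patients have left 560 mg and do not fit the 560-to-420 mg step. Neuropathy is the only clean route to it.

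**3. Does the sentence about patients already at 1.2 mg/kg settle it?**

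That sentence follows the step for recurrence despite ibrutinib reduction. At the second Grade 4 event this rule has not yet reduced ibrutinib, so the sentence does not reach that step. A third Grade 4 event, after the cut to 420 mg, can be read as a recurrence despite reduction. The patient would then have three candidate instructions: 1.8 mg/kg (the step), 1.2 mg/kg (the default against re-escalation), or stop both drugs.

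**4. Size for an affected patient**

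- Ratio: 1.8 / 1.2 = 1.5, a 50% higher dose.
- Difference: 1.8 − 1.2 = 0.6 mg/kg.
- At 40 kg (Section 3.1 requires more than 40 kg): 72 − 48 = 24 mg per infusion.
- At the 100 kg dosing cap (Section 5.1.1): 180 − 120 = 60 mg per infusion.

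The milligram figures are before the rounding that Section 5.1.1 allows.

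**The case against.** The strongest reply is that Section 6.2 already supplies the answer. Its closing clause covers every dose in the section and gives both a default (stay reduced) and a decision-maker (the PI). The two steps read as if drafted for a patient on starting doses. They pair 1.8 mg/kg with ibrutinib 560 mg, and their point is to say which drug to cut, in line with the opening of Section 6.2. Fixed ibrutinib figures appear elsewhere in the section and also fail to fit some patients, such as one who started at 420 mg in the lead-in. A site reading the section as a whole would probably stay at 1.2 mg/kg or ask the PI.

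The affected group is also narrow. It needs earlier Grade 2 or 3 neuropathy, ibrutinib still at 560 mg, and a second Grade 4 anemia or thrombocytopenia event. Section 2.4.1 reports platelet shifts to Grade 3 or worse in 6% of patients in the single-agent BV phase 2 studies. The rate for the combination is unknown.

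Most of this stands as a description of likely intent and limited reach. It also rules out a stronger reading that a reader might infer, namely that the protocol orders re-escalation without qualification. The closing clause qualifies it. What remains is that the clause is worded as a general default while the two steps are unconditional, and nothing says which prevails. A site that lets the specific instruction override the general one would be following the text.

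**Conclusion.** The point holds as a minor patient-safety correction. Two of the eight BV restart steps meant to leave BV unreduced name a fixed dose. For a patient reduced to 1.2 mg/kg for neuropathy, the first of them literally gives a 50% increase, against the section's own default. The third-occurrence step has the same fault and may overlap with the instruction to stop both drugs.

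The harm is bounded. Section 5.1.1 makes 1.8 mg/kg the protocol dose, and Section 2.1 gives it as the single-agent MTD. Neuropathy must have improved to Grade 1 or baseline before BV restarted at 1.2 mg/kg, and new or worsening Grade 2 or 3 neuropathy triggers another hold and a restart at 1.2 mg/kg.

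Three wider readings are tempting but not supported:

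- That every other restart step in Section 6.2 keeps the dose level. The neuropathy rule and the final cytopenia step restart at 1.2 mg/kg.
- That the sentence on patients already at 1.2 mg/kg certainly excludes the third occurrence. The text leaves this open.
- That the trial's inference is affected. The sample size, error rates, Simon boundaries and complete-response endpoint do not depend on this wording.

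The 50% figure assumes that a site follows the step literally. The documents give no basis for a patient count, though it is probably small.

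**What to change.** In the second-Grade-4 and third-occurrence sentences of the anemia/thrombocytopenia rule, replace the fixed 1.8 mg/kg restart with *at the same BV dose level*. This is the form used in the rest of the section, and it matches the stated preference for reducing ibrutinib first. Any return to 1.8 mg/kg then stays with the PI under the closing clause. Nothing changes for patients still at 1.8 mg/kg.

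The clinical team should confirm the wording. In the same edit they should say whether a third Grade 4 event in a patient already at 1.2 mg/kg means resuming at that dose or stopping both drugs.

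The cost is a small wording change in the next protocol amendment, with no added patients, visits or procedures.

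### Section 6.2 gives two contradictory ibrutinib restart doses after Grade 4 non-hematologic toxicity at a 560 mg start, and does not say which governs

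*Combined protocol and SAP*

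**What the plan says.** Section 6.2 (Dose Modifications) opens with a general principle: ibrutinib is reduced before BV, except for neuropathy. Ibrutinib doses are then prescribed in two places.

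**Ibrutinib bullets (Interrupt or discontinue therapy).** The trigger is "Interrupt therapy for any non-hematological toxicity" of Grade 3 or higher, Grade 3 or higher neutropenia with infection or fever, "or Grade 4 hematological toxicities". The steps are:
- First event: "Reinitiate ibrutinib at the starting dose (indicated specific) once toxicities have resolved to Grade 1 or baseline (recovery".
- Recurrence: "If the toxicity reoccurs, reduce dose by 1 capsule (140 mg/day".
- Next: "A second reduction of dose by 140 mg may be considered as needed".
- End: "Discontinue if these toxicities persist or recur following 2 dose reductions".

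**BV block (Brentuximab vedotin, commercial supply).** This block also prescribes ibrutinib doses.
- *Other non-hematological toxicities.* First Grade 4: "then resume treatment at same dose level but reduce ibrutinib dose from 560 mg to 420 mg". Second Grade 4: "then resume BV at same dose level but reduce ibrutinib from 420 mg to 280 mg". A third Grade 4 event stops ibrutinib. For Grade 3, the first event resumes at the same dose, the second goes from 560 to 420 mg and the third from 420 to 280 mg.
- *Anemia and thrombocytopenia.* The first Grade 4 event resumes at the same dose, the second goes from 560 to 420 mg and the third from 420 to 280 mg.
- *After the ibrutinib reductions.* For both groups, further recurrence lowers BV to 1.2 mg/kg. Both drugs stop if BV is already at 1.2 mg/kg.

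The Synopsis gives 560 mg as the expected phase II dose. Section 5.1.7 starts the lead-in at 420 mg, and that dose goes forward if 560 mg is not tolerated.

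**The concern.** A Grade 4 non-hematologic toxicity meets both triggers, and the two restart doses cannot both be followed. The contradiction arises at the first such event, so no recurrence is needed, and it arises at the expected phase II dose.

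The section layout does not help. A site looking up the ibrutinib dose under the ibrutinib heading restarts at 560 mg after a life-threatening event. A site reading on into the BV block restarts at 420 mg. Each follows printed text, and a monitor could not say which had deviated.

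The trial has four participating sites, and Section 5.1.7 cites possible overlapping toxicity as the reason for starting at 420 mg. What is at stake is the safety of re-exposure and a consistent description of tolerability, which is a secondary objective.

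**Working it through.** The plan states no figure to reproduce here, so the check is a trace of the printed steps. It assumes that each rule is followed throughout, that the events are successive occurrences of the same kind, and that each resolves far enough to restart. One capsule is 140 mg.

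**1. Ibrutinib dose after each event, 560 mg start**

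| Event | Ibrutinib bullets | BV block | Comparison |
|---|---|---|---|
| Grade 4 other non-hematologic, 1st | 560 | 560 − 140 = 420 | 140 mg apart (140/560 = 25%) |
| 2nd | 560 − 140 = 420 | 420 − 140 = 280 | 140 mg apart (140/420 = one third) |
| 3rd | 420, or optionally 420 − 140 = 280 | stop | continue versus stop |
| Grade 3 other non-hematologic, 1st / 2nd / 3rd | 560 / 420 / 420 or 280 | 560 / 420 / 280 | compatible |
| Grade 4 anemia or thrombocytopenia, 1st / 2nd / 3rd | 560 / 420 / 420 or 280 | 560 / 420 / 280 | compatible |

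In the last two rows the third steps are compatible because the bullets make the second cut optional. A site giving 280 mg obeys both rules. The contradiction in dose steps is therefore confined to Grade 4 non-hematologic toxicity other than neuropathy.

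**2. After two reductions.** For Grade 3 non-hematologic toxicity and Grade 4 anemia or thrombocytopenia, the bullets discontinue ibrutinib on the next recurrence. The BV block lowers BV to 1.2 mg/kg and stops both drugs only if BV is already there. These are different actions on different drugs.

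**3. Recovery level.** For a first Grade 4 anemia or thrombocytopenia, the bullets require Grade 1 or baseline before restart. The anemia and thrombocytopenia paragraph requires Grade 2 or lower, or baseline. For a first Grade 4 non-hematologic event both require Grade 1 or baseline, so there only the restart dose differs.

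**4. 420 mg start.** The bullets give 420, then 420 − 140 = 280, then 280 or optionally 280 − 140 = 140 mg. The first cut in the BV block is printed as 560 to 420 mg and cannot be applied literally to a patient already on 420 mg. The later 420 to 280 mg step can.

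**5. Is a ranking stated?** The opening of Section 6.2 says which drug to reduce first, not which ibrutinib schedule applies. The paragraph on holding both drugs deals with timing. The closing text deals with delays and re-escalation. None of it ranks the two rules.

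**The case against.** The strongest defense is that the specific rule prevails over the general one. The bullets would be the default, and the BV block would apply wherever it prints a step for a given toxicity and grade. This fits the stated preference for reducing ibrutinib and resolves the Grade 4 conflict in favor of 420 mg. It is a sensible reading, and the fix below adopts it. But it is not written, and the specific steps sit under the other drug's heading.

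Three limiting points stand:
- Under either rule, ibrutinib is held after a first Grade 4 non-hematologic event until Grade 1 or baseline, so the difference there is one capsule at restart.
- The recovery-level difference is softer than the dose conflict. The Grade 2 level could be meant for BV and the Grade 1 level for ibrutinib, since the next cycle waits until toxicity is acceptable for both drugs. That text names no grade.
- The documents give no Grade 4 non-hematologic rate for the combination, so the number of patients affected cannot be stated and may be small.

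A reader might infer more than the documents support:
- *That the two schedules conflict throughout.* The trace shows compatible steps through event 3 for two of the three event types.
- *That a patient starting at 420 mg has no rule.* The one-capsule cut in the bullets gives 280 mg.
- *That the bullets are superseded.* The neutropenia paragraph refers to an ibrutinib reduction specified elsewhere and prints none, so it depends on them.

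**Conclusion.** The contradiction is real and should be corrected. For Grade 4 non-hematologic toxicity other than neuropathy at a 560 mg start, the printed rules give 560 / 420 / (420 or 280) mg against 420 / 280 / stop, with no order of precedence. If 560 mg goes forward, this wording applies to all 39 planned phase II patients, although only those who have such an event would be affected.

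The different actions after two reductions, the recovery level for a first Grade 4 anemia or thrombocytopenia, and the wording for a 420 mg start are secondary defects in the same text.

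A reader might take this as a threat to the primary result. It is not one on these documents. The complete response definition, the two-stage boundaries (at least 7 of 19, then 17 of 39) and the error rates do not depend on the restart rule. This is a safety wording correction.

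**What to change.** Amend Section 6.2 as follows.

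1. **Precedence.** Where the BV block prints an ibrutinib step for a given toxicity and grade, that step governs over the ibrutinib bullets. The bullets govern all other events, including neutropenia. A first Grade 4 non-hematologic toxicity then restarts one capsule lower and a third stops ibrutinib, in line with the section's opening principle. The precedence must be limited in this way, because the bullets hold the only ibrutinib dose rule for neutropenia.
2. **Relative steps.** Reword each ibrutinib cut in the BV block as one 140 mg capsule below the current dose. For Grade 4 non-hematologic events this gives 420 / 280 / stop from 560 mg and 280 / 140 / stop from 420 mg. The sponsor should confirm 140 mg as the lowest dose. The bullets already allow it from a 420 mg start (420 − 2 × 140 = 140).
3. **After two reductions.** State one action: either stop ibrutinib, or lower BV to 1.2 mg/kg with ibrutinib continued.
4. **Recovery level.** State one level for restart after a first Grade 4 anemia or thrombocytopenia, or say explicitly which level applies to which drug.

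The cost is a wording amendment and a notice to sites. No patients, visits or procedures are added, and the statistical section does not change.
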